1.2 Therapeutic Rationale for ADX-102 in Sjögren-Larsson Syndrome

1.3 Clinical Trials of ADX-102

1.3.1 Sjögren-Larsson Syndrome

Study NS-003 was a randomized, double-blind, vehicle-controlled, parallel group Phase 2 clinical trial evaluating the activity of ADX-102 1% topical dermal cream at a dose of 8 mg/cm² in subjects with ichthyosis associated with SLS.

A total of 12 male and female subjects aged 6 years or older (range 8 to 25 years) with genetically confirmed SLS and active ichthyosis on the lower extremities that was determined to be of moderate severity or higher were enrolled and randomized 1:1 to ADX-102 1% or vehicle. Subjects received study drug (ADX-102 1% or vehicle) once daily for 8 weeks.

The target area for treatment was an area on the lateral aspect of the lower leg, up to approximately 10 inches in height by 4 inches wide. In the cases where the lower leg did not have an ideal target area for treatment, the Investigator chose an area on another portion of the body as the target area. The lower leg was not utilized in only one subject whose right upper back was identified by the Investigator as the target treatment area.

In this Phase 2 clinical trial, the reduction in the severity of the ichthyosis in ADX-102-treated subjects was statistically significant relative to baseline. The most common reduction in the severity of the ichthyosis (assessed by the scaling ISS sub-score) in ADX-102-treated subjects over the duration of drug exposure (eight weeks) was one point from a median baseline severity of 3, representing an average change from moderate to mild disease. In addition, the activity of drug was statistically superior to that of vehicle. ADX-102-treated subjects showed greater mean and percentage decreases from baseline, and a higher proportion of ADX-102-treated subjects exhibited favorable individual responses than that of the vehicle-treated subjects for all the ISS sub-scores, except for excoriations.

ADX-102 1% w/w topical dermal formulation was generally well-tolerated and there were no significant or serious adverse events (SAE), or treatment-emergent adverse events (TEAEs) that led to treatment discontinuation.

pattern of changes was observed with ADX-102 for chemistry analytes, hematology parameters, or vital signs.

Overall, the results of Study NS-003 demonstrated that the ADX-102 1% w/w topical dermal formulation was safe and well-tolerated, and improved SLS ichthyosis in a clinically and statistically significant manner superior to that of vehicle.

No

1.3.2 Ocular Indications

As a topical ocular formulation, ADX-102 was safe and well-tolerated in a Phase 1 clinical trial and demonstrated efficacy and safety in Phase 2 clinical trials in allergic conjunctivitis and noninfectious anterior uveitis.

Please refer to the Investigator's Brochure for additional information.

1.4 Minimization of Risk

In the Phase 2 clinical trial in SLS patients (NS-003), 8 weeks of daily application of ADX-102 1% w/w topical dermal formulation over ~3% body surface area (BSA) has been shown to be safe and well-tolerated.

ADX-102 has been well-tolerated in multiple nonclinical, single dose and repeat dose pharmacology and toxicology studies in mice, rats, rabbits, dogs, and non-human primates, via topical dermal (TD), topical ocular (TO), oral (PO), intraperitoneal (IP), subcutaneous (SC), and intravenous (IV) routes of administration. Of particular relevance to TD application, Good Laboratory Practice (GLP) studies testing up to ADX-102 5% topical dermal cream have shown that TD administration of ADX-102 to Göttingen minipigs for 21 days and nine weeks was well-tolerated, with no local or systemic adverse effects observed. In a standard battery of genotoxicity tests, ADX-102 was non-mutagenic and non-clastogenic. Furthermore, in vivo central nervous system (CNS), respiratory, and cardiovascular safety pharmacology studies showed no adverse effects with ADX-102. Please refer to the Investigator's Brochure for additional information.

The Phase 3 study design includes an assessment of increasing BSA treatment (Part 1) lasting 24 weeks in approximately 9 eligible subjects receiving ADX-102 1% or vehicle topical dermal cream initially over approximately 20% BSA then increasing to up to 90% BSA. The assessment in Part 1 will allow for real-time evaluation of the safety and effectiveness of ADX-102 1% relative to vehicle treatment dosed over longer durations and greater BSA than in the Phase 2 study. After completion of Part 1 of the Phase 3 study, a separate set of eligible subjects will be enrolled into Part 2 that allows for the assessment of the safety of vehicle relative to ADX-102 1% treatment on all areas of ichthyosis.

In addition, an independent Data Safety Monitoring Board (DSMB) will be established to review all available safety data after approximately 9 subjects have completed study Week 24 in Part 1. Additional DSMB reviews will occur approximately every 6 months throughout the trial, or as deemed necessary by the DSMB or Sponsor to ensure subject safety and well-being. The assessment of safety will be determined from dermatological endpoints, vital sign measurements, physical examinations, hematology and chemistry laboratory testing, cardiac monitoring, use of concomitant medications, and review of adverse events (AEs). Refer to Section 3.4.1.

1.5 Potential Benefit

As described above, SLS ichthyosis is generally recalcitrant to therapy. Phase 2 clinical trial results in SLS patients treated over ~3% BSA with ADX-102 1% for 8 weeks demonstrated that ADX-102 was effective in treating the ichthyosis associated with SLS.

The Phase 3 study will assess he activity of ADX-102 1% after 24-weeks of dosing over all skin area affected by ichthyosis (approximately 80 – 90% BSA in a typical SLS patient).

1.6 Rationale for Dose Selection

It has been shown that free aldehydes are cytotoxic. In one study, free all-trans-retinal resulted dose-dependent cell death of ARPE19 cells, with complete or nearly complete cell death observed at 10 μ M (5). A similar phenomenon was observed in HEK293 cells. Since tissue necrosis is not evident in the skin of SLS patients, the theoretical maximum aldehyde concentration likely less than 10 μ M. Because ADX-102 binds aldehydes with a 1:1 stoichiometry, maximal drug target levels in skin are 10 μ M. GLP nonclinical studies in Göttingen minipigs have shown that once-daily application of 1% w/w ADX-102 topical dermal cream results in ADX-102 skin concentrations that meet or exceed this target. The Phase 2 clinical trial results confirmed the activity of once-daily ADX-102 1% administration.

2 STUDY OBJECTIVES AND ENDPOINTS

2.1 Study Objectives

2.1.1 Primary Objective

To evaluate the efficacy of ADX-102 1% topical dermal cream on ichthyosis associated with SLS.

2.1.2 Secondary Objective

To evaluate the safety and secondary efficacy endpoints of ADX-102 1% topical dermal cream in subjects with SLS.

2.2 Study Endpoints

2.2.1 Primary Endpoint

The primary efficacy endpoint is the Visual Index for Ichthyosis Severity (VIIS) scaling severity score as assessed by the Investigator in the target efficacy area.

3 INVESTIGATIONAL PLAN

3.1 Overall Study Design and Plan

This is a two-part, randomized, double-blind, vehicle-controlled, parallel-group Phase 3 clinical trial with an initial assessment of increasing BSA treatment (Part 1). After the completion of Part 1, a separate set of eligible subjects will be enrolled into Part 2.

Part 1 Design:

Part 1 will evaluate the safety, tolerability, and efficacy of treatment to the affected area of ichthyosis initially on approximately 20% BSA and then increasing up to 90% BSA over 24 weeks of exposure and will confirm an appropriate sample size for Part 2.

Subjects will be consented and screened for eligibility. Approximately 9 subjects will be randomized in a 2:1 ratio to receive ADX-102 1% or vehicle.

Subjects or caregivers will apply study drug (i.e., ADX-102 1% or vehicle) to a treatment area identified by the Investigator.

The initial treatment area will be defined as approximately 20% BSA with Grade 2 or higher on the VIIS scaling severity score, as assessed by the Investigator, and will include one of the body sites as defined in the VIIS tool (target efficacy area).¹ From Week 1 through Week 12, subjects will receive treatment once daily in the initial treatment area only.

If the Investigator determines that there are no safety or tolerability issues at the end of Week 12, the treatment area will increase to all of the affected areas of ichthyosis on one-half of the body (approximately 40-45% BSA in a typical SLS patient). From Week 13 through Week 20, subjects will receive treatment once daily on the expanded treatment area.

If there are still no safety or tolerability issues at the end of Week 20, the treatment area will further increase to all affected areas of ichthyosis on the entire body (approximately, 80-90% BSA in a typical SLS patient). Subjects will receive treatment once daily treatment on all affected areas from Week 21 through Week 24.

Subjects completing the 24 weeks of study drug treatment will then be monitored for an additional 4 weeks for safety.

Subjects who are randomized in Part 1 will not be eligible to participate in Part 2.

¹ Dorsal foot cannot be selected as the target efficacy area.

Part 2 Design:

Part 2 will evaluate the safety, tolerability, and efficacy of treatment to the affected area of ichthyosis on the body (approximately 80-90% BSA in a typical SLS patient) over 24 weeks of exposure.

Subjects will be consented and screened for eligibility. Qualified subjects will be randomized in a 2:1 ratio to either ADX-102 1% or vehicle. The appropriate sample size for Part 2 will be confirmed in Part 1. Subjects or caregivers will apply study drug (i.e., ADX-102 1% or vehicle) once daily to all affected areas of ichthyosis on the body (approximately 80 – 90% of BSA in a typical SLS patient).

The target efficacy area for all efficacy analyses at Week 24 will be one of the body sites as defined in the VIIS tool with Grade 2 or higher on the VIIS scaling severity as assessed by the Investigator.¹

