4.3 Subject Withdrawal and Replacement

Subjects and caregivers will be informed that they have the right to withdraw the subject from the study at any time for any reason, without prejudice to their medical care. The Investigator also has the right to withdraw subjects from the study for any of the following reasons:

- Progression of disease that, in the opinion of the Investigator, precludes further study drug treatment,
- Development of an unacceptable AE or SAE,
- Subject or Sponsor request,
- Subject non-adherence to study drug dosing or protocol requirements, or
- Pregnancy.

The reason for study withdrawal is to be documented in the subject's source documents and CRF. Withdrawn subjects may be replaced at the discretion of the Sponsor.

Subjects who prematurely discontinue from the study should be seen as soon as possible for Week 24 assessments (Part 1:Table ; Part 2:Table 2).

For subjects who are lost to follow-up (i.e., those subjects whose status is unclear because they fail to appear for study visits without stating an intention to withdraw), the Investigator should show due diligence by documenting in the source documents all steps taken to contact the subject (e.g., dates of telephone calls, registered letters, etc.).

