6.5 Adverse Events

AEs will be collected from the time the subject signs the informed consent form through 30 days after the last dose of study drug. AEs must be recorded in the subject's CRF. The Sponsor and Investigator or qualified study personnel will review and evaluate adverse events on an ongoing basis. See Section 9 for further detail on AE reporting.

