7.7 Visit 7 (Week 20 ± 5 days) – Site Visit

- Collect Patient/Observer-reported scales (Section 6.11)
- Collect study drug supply and diary (Sections 6.18.1 and 6.18.2)
- Record concomitant medications and adverse events (Sections 6.4 and 6.5)
- Collect urine sample for urinalysis and pregnancy test, if applicable (Sections 6.15.1.3 and 6.15.1.4)
- 12-lead ECG (Section 6.6)
- Collect vital signs (Section 6.7)
- Symptom-directed physical exam (Section 6.8)
- Complete dermatologic examination (Section 6.12)
- Take digital photography (Section 6.13)
- Complete VIIS (Section 6.9)
- Complete Global Impression of Severity (Section 6.10)
- PD sample collection (Section 6.14)
- Collect blood samples for hematology and chemistry (Sections 6.15.1.1 and 6.15.1.2)
- PK sample collection (blood and urine) (Section 6.16)
- Apply study drug to target treatment area¹ (Section 5.6)
- Dispense study drug supply and diary (Sections 6.18.1 and 6.18.2)

7.8 Visit 8 (Week 24 ± 5 days) – Early Termination – Site Visit

- Collect Patient/Observer-reported scales (Section 6.11)
- Collect study drug supply and diary (Sections 6.18.1 and 6.18.2)
- Record concomitant medications and adverse events (Sections 6.4 and 6.5)
- Collect urine sample for urinalysis and pregnancy test, if applicable (Sections 6.15.1.3 and 6.15.1.4)
- 12-lead ECG (Section 6.6)

¹ If treatment area will be expanded up to 90% BSA, Investigator should apply study drug to this expanded treatment area during the visit but after the collection of pre-dose PK samples.

- Collect vital signs (Section 6.7)
- Symptom-directed physical exam (Section 6.8)
- Complete dermatologic examination (Section 6.12)
- Take digital photography (Section 6.13)
- Complete VIIS (Section 6.9)
- Complete Global Impression of Severity (Section 6.10)
- PD sample collection (Section 6.14)
- Collect blood samples for hematology and chemistry (Sections 6.15.1.1 and 6.15.1.2)
- PK sample collection (blood and urine) (Section 6.16)

7.9 Visits 9 (Week 28 ± 3 days) – Safety Follow-up - Home Visit (Section 6.19)

- Record concomitant medications and adverse events (Sections 6.4 and 6.5)
- Complete dermatologic examination (Section 6.12)
- Take digital photography (Section 6.13)

8 STUDY ACTIVITIES FOR PART 2

Study activities for Part 2 are summarized in the Study Activities Schedule (Table 2).

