8.8 Visit 7 (Week 20 ± 3 days) – Telephone Check-In (Section 6.20)

• Record concomitant medications and adverse events (Sections 6.4 and 6.5)

8.9 Visit 8 (Week 24 ± 5 days) – Early Termination – Site Visit

- Collect Patient/Observer-reported scales (Section 6.11)
- Record concomitant medications and adverse events (Sections 6.4 and 6.5)
- Collect urine sample for urinalysis and pregnancy test, if applicable (Sections 6.15.1.3 and 6.15.1.4)
- 12-lead ECG and Holter monitoring (Section 6.6)
- Collect vital signs (Section 6.7)
- Symptom-directed physical exam (Section 6.8)
- Complete dermatologic examination (Section 6.12)
- Take digital photography (Section 6.13)
- Complete VIIS (Section 6.9)
- Complete clinician-reported global impression of severity scale (Section 6.10)
- PD sample collection (Section 6.14)
- Collect blood samples for hematology and chemistry (Sections 6.15.1.1 and 6.15.1.2)
- PK sample collection (blood and urine) (Section 6.16)
- Collect study drug supply and diary (Sections 6.18.1 and 6.18.2)
- Conduct Subject Exit Interview¹ (Section 6.21)

8.10 Visit 9 (Week 28 ± 5 days) – Safety Follow-up – Site Visit

- Collect Patient/Observer-reported scales (Section 6.11)
- Record concomitant medications and adverse events (Sections 6.4 and 6.5)
- Complete dermatologic examination (Section 6.12)
- Take digital photography (Section 6.13)

¹ Subject Exit Interview should be conducted within 30 days of the scheduled visit.

- Complete VIIS (Section 6.9)
- Complete Global Impression of Severity (Section 6.10)

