9 ADVERSE EVENT REPORTING

AEs will be collected from the time the subject signs the informed consent form through 30 days after the last study drug administration.

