9.1.5 Reporting Serious Adverse Events

The Investigator is responsible for reporting all SAEs, regardless of causality, to the Sponsor designee within 24 hours of learning of the occurrence. SAEs should be sent to:

(Local toll-free numbers will be provided on the SAE report form cover sheet.)

The reporting timeframe starts when the subject signs the informed consent or assent form through 30 days after the last study drug administration. At a minimum, a description of the event and the Investigator's judgment of causality must be provided at the time of the initial report. These preliminary reports will be followed by detailed descriptions that will include copies of hospital case reports, autopsy reports, and other documents when requested and applicable.

A follow-up SAE Report must be submitted within 24 hours of the Investigator receiving the follow-up information (such as information regarding complications, progression or resolution).

An SAE that is considered completely unrelated to a previously reported event should be reported separately as a new SAE.

The procedures for reporting SAEs are as follows:

- Complete the "Serious Adverse Event Report Form." The Investigator may contact Pharmacovigilance via the telephone hotline for assistance with SAE reporting.
- Fax or email the SAE Form to the attention of Pharmacovigilance within 24 hours of the Investigator's knowledge of the event.

The original copy of the SAE Report Form and the fax confirmation sheet (or email) must be kept with the source documentation at the study site.

Follow-up information should be communicated the same way, using a new SAE Report Form stating that it is a follow-up to the previously reported SAE and giving the date of the original report. The follow-up information should describe whether the event has resolved or continues, if and how it was treated, and whether the subject continued or withdrew from study participation.

The Investigator and study personnel should institute any supplemental investigations of SAEs based on their clinical judgment of likely causative factors. This may include clinical laboratory

tests not specified in the protocol, histopathologic examinations, or consultations with specialists. The Sponsor or their designee may also request the Investigator to conduct supplemental assessments.

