8.4. KEY DEFINITIONS AND TERMINOLOGY

Reference start date and study day

Study Day will be calculated from the reference start date and will be used to show start/stop day of assessments and events.

Baseline Value

For purposes of analysis, the baseline value is defined as the last non-missing value obtained prior to initiation of study drug.

Change from Baseline.

Change from baseline for a given endpoint is defined as the difference between a post-treatment study day value and the baseline variable value and will be calculated directionally as post-study minus baseline.

Note that for the VIIS, it is planned that a single investigator will complete this instrument prior to randomization on day 1 of Part 1.

Day 1 (Baseline)

Day 1 is the earliest day that the study drug is first initiated.

Age

Syneos Health #1009367

Age is calculated as the number of whole years from a subject's date of birth to the date of informed consent.

Study Visit.

Study visit is the nominal visit as recorded on the eCRF.

Total Days on Study

Total days on study is defined as the number of days from Day 1 to the date of completion or early termination.

Last Dose of study drug

Last dose of study drug is defined as the number of days from day 1 to the date of last dose of study drug.

Duration of SLS.

The duration of SLS is defined as the number of whole years from the date of onset of SLS diagnosis to the date of informed consent.

Adverse Event

An adverse event is any untoward medical occurrence in a patient or clinical investigation patient, temporally associated with the use of a medicinal product, whether or not considered related to the medicinal product.

Treatment Period

The Treatment Period covers the duration that a patient is in the study from Baseline (Day 1) to Week 24.

Safety Follow-up Period

The Safety Follow-up Period continues for 28 days after the last dose of study treatment at Week 24 through Week 28.

Definition of Study Completion

A patient will be defined as "completed" if she or he completes the Week 24 study visit.

End of Study Definition

Syneos Health #1009367

End of study is defined as the date when the patient has completed one of the following: completed the follow-up visit after the Week 24 visit, permanently discontinued from the study, or lost to follow-up.

Day of Study Termination

Day of study termination = Termination Date - Date of Baseline (Day 1) + 1.

Percent Change from Baseline

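### AEs are to be collected to 30 days after the last dose, but the schedule does not secure this: nothing follows the early-termination visit, and completers' follow-up is 28 days

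*Protocol*

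**What the plan says.** - **Collection window.** Protocol section 6.5: "AEs will be collected from the time the subject signs the informed consent form through 30 days after the last dose of study drug". The opening of section 9 repeats the limit ("through 30 days after the last study drug administration"), and section 9.1.5 applies it to SAEs: "The reporting timeframe starts when the subject signs the informed consent or assent form through 30 days after the last study drug administration". None of these makes an exception for subjects who stop early.
- **Follow-up of completers.** The Part 1 text of section 3.1: "Subjects completing the 24 weeks of study drug treatment will then be monitored for an additional 4 weeks for safety". Section 3.5 gives a 4-week follow-up period for both parts. The headings of sections 7.9 and 8.10 place the visit by study week: "Visits 9 (Week 28 ± 3 days" in Part 1 and "Visit 9 (Week 28 ± 5 days" in Part 2. Visit 8 is at Week 24 with a 5-day window either side in both parts.
- **Follow-up of early leavers.** Section 4.3: "Subjects who prematurely discontinue from the study should be seen as soon as possible for Week 24 assessments". Footnote 2 of Tables 1 and 2 asks for the Visit 8 procedures where feasible. No later visit or call is assigned to them. The end-of-study definition in SAP section 8.4 includes subjects who have "permanently discontinued from the study, or lost to follow-up".
- **Anchor of Visit 9.** Tables 1 and 2 use study weeks. Protocol section 5.6 counts the Part 2 safety visit from the end of dosing. SAP section 8.4 describes the Part 1 follow-up period both as 28 days from the last dose and as Week 24 to Week 28.
- **TEAE window.** SAP section 11.2 closes it at 28 days after the last dose, or sooner if certain events occur. Protocol section 9.1.2 gives no closing date.
- **Dosing at Visit 8.** Protocol Table 1 has no administration entry at Visit 8, and SAP Table 4.1.1 has one. Protocol Table 1-1 lists post-dose measurements at that visit.

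**The concern.** A collection window needs a contact at or after its close; otherwise events late in the window are recorded only if someone volunteers them. Here the window is the same for all subjects but the scheduled contacts are not.

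Subjects who stop early include those withdrawn for an unacceptable AE (section 4.3), those unblinded (section 3.3.2) and those who become pregnant (section 9.1.8). The more promptly a site arranges their early-termination visit, the less post-treatment time that visit covers.

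The groups are small: 6 active subjects planned in Part 1 (Synopsis, Statistical Analysis) and 20 in Part 2 (section 10.1). One subject with an unrecorded event changes active-arm incidence by 1/6 = 17 percentage points or 1/20 = 5 percentage points. The Part 1 safety data also go to the DSMB for its advice on continuing (section 3.4.1).

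**Working it through.** **Inputs.** AE window: 30 days from last dose (sections 6.5, 9, 9.1.5). Visit 8: Week 24 ± 5 days in both parts. Visit 9: Week 28 ± 3 days in Part 1 and ± 5 days in Part 2 (Tables 1 and 2). TEAE window: 28 days from last dose (SAP section 11.2).

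**Step 1: the plan's own figure.** (28 − 24) × 7 = 28 days, which reproduces the 4-week follow-up in section 3.5. Against the AE window, 30 − 28 = 2 days (7%) come after the last contact even when both visits are on schedule.

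**Step 2: completers, dosing up to Visit 8.** Shortest in-window gap = 28 − (days Visit 8 is late) − (days Visit 9 is early).
- Part 1: 28 − 5 − 3 = 20 days, so 30 − 20 = 10 days (33%) are uncovered.
- Part 2: 28 − 5 − 5 = 18 days, so 30 − 18 = 12 days (40%) are uncovered.
- Longest gaps: 28 + 8 = 36 days and 28 + 10 = 38 days, so an in-window Visit 9 can also fall after day 30.
- If the last dose is the day before Visit 8, each gap lengthens by one day: 29 days on schedule, with minima of 21 and 19.

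**Step 3: completers, Visit 9 counted from the end of dosing.** The same result follows if dosing stops at nominal Week 24. Only the Visit 9 window then matters.
- Part 1: 28 − 3 = 25 to 28 + 3 = 31 days; worst shortfall 5 days (17%).
- Part 2: 28 − 5 = 23 to 28 + 5 = 33 days; worst shortfall 7 days (23%).

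**Step 4: the SAP's 28-day TEAE window.** On schedule the shortfall is 28 − 28 = 0. At the Step 2 minima it is 28 − 20 = 8 days (29%) and 28 − 18 = 10 days (36%). An AE that starts on day 29 or 30 is collected under the protocol but is not counted as a TEAE in the SAP tables.

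**Step 5: early leavers.** If the early-termination visit takes place d days after the last dose, 30 − d days have no scheduled contact: all 30 if the visit is on the day of the last dose. Other rules cover part of that time:
- Section 9.1.6 follows AEs already known, to stabilization, resolution or database lock.
- Section 6.15.1 follows clinically significant laboratory results back to normal or baseline.
- Section 9.1.8 follows pregnancies to outcome.
- Section 9.1.5 asks for notification of deaths and SAEs after withdrawal that may be drug-related, within 30 days of the last dose. The same section asks for all SAEs whatever the cause, so its two statements differ for withdrawn subjects.

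What remains is the new-onset non-serious AE after the early-termination visit. It falls inside the section 6.5 window, and no planned contact would find it.

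**The case against.** The strongest defence is that the subjects of most concern are not abandoned. An early-termination visit is specified, with AE review, laboratory tests, ECG, vital signs and a dermatologic examination. The harm that led to withdrawal is then followed under section 9.1.6, and laboratory findings, pregnancies and possibly related deaths or SAEs have their own rules. That stands, and it confines the gap for early leavers to new events after that visit. A reader might infer that early leavers have no safety contact at all after treatment; the documents do not say that.

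Second, section 5.6 and SAP section 8.4 do link follow-up to the end of dosing or the last dose, so it would be wrong to say that Visit 9 is simply timed from Day 1. That also stands. The fault is that the documents disagree about the anchor.

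Third, 20 and 18 days need Visit 8 at its latest, Visit 9 at its earliest, and dosing up to that late Visit 8. The last condition is not stated, and the Visit 8 dosing entries conflict. The figures are limits, not expected values.

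Fourth, a reader might infer that late AEs will be under-counted in the drug arm. The documents give no discontinuation counts by arm. The interruptions for laboratory findings in SAP section 8.6 are not shown to be early departures; SAP section 9.2.1 says many of those subjects still received the full course. Unequal capture by arm is a possibility only.

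Fifth, scope. The sentence limiting follow-up to completers is Part 1 text, and the SAP covers Part 1 only (its section 2). For Part 2 the early-leaver gap is inferred from Table 2 footnote 2 and section 4.3. The SAP end-of-study definition serves the analysis and does not cancel the 30-day collection rule.

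**Conclusion.** The point holds in limited form. The protocol sets a 30-day collection window for everyone, and its schedule does not guarantee a contact that closes it.

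- **Early leavers:** up to 30 of 30 days have no scheduled contact after the early-termination visit, depending on how soon that visit takes place. The exposure is to new non-serious AEs.
- **Completers:** 2 days short on schedule. The worst in-window shortfall is 10 days (Part 1) or 12 days (Part 2) if dosing continues to a late Visit 8, and 5 or 7 days if Visit 9 is counted from the end of dosing.
- **Consistency:** the Visit 9 anchor, the Visit 8 dosing entries, and the 28-day TEAE and 30-day collection windows need to be reconciled.

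The completer figures assume that visits stay within their windows; SAP section 8.6 records that some did not, so actual gaps may differ either way. No direction or size of bias between arms can be derived from the documents. The change is worth making because it is cheap and lets the schedule deliver what the protocol already requires.

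**What to change.** 1. In Protocol sections 3.1 and 4.3 and Tables 1 and 2, require a final AE contact for every dosed subject, including early terminators, at the close of the protocol's own 30-day window, counted from the actual last dose. A telephone check-in under section 6.20 is enough. It is needed only where Visit 9 falls earlier or does not occur.
2. State one anchor for Visit 9 and use it in Tables 1 and 2, section 5.6 and SAP section 8.4. Reconcile the Visit 8 dosing entries in Protocol Tables 1 and 1-1 and SAP Table 4.1.1, so that the date of last dose is unambiguous.
3. Align the TEAE window in SAP section 11.2 with the AE collection window. Otherwise events found on days 29 and 30 would still be left out of the TEAE tables.
4. In SAP section 8.4, align the end of study for discontinued subjects with the final AE contact.

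The cost is wording in both documents, plus one call for each early leaver and each completer whose Visit 9 comes before day 30. The call procedure already exists.
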